All participants will be provided with ample time to ask questions prior to enrolling in the study. As noted above, a series of questions will assess participants' understanding of the study in order to ensure that participants have adequately comprehended the critical information (e.g., risks/benefits, voluntary nature) and are able to complete the consent process. Participants will be clearly informed that the study is voluntary and that they can withdraw from the study at any time, with no penalty. Additionally, all research staff have been trained in human subjects research. The main risk to participating in the study is potential emotional discomfort during the assessments. ACT-MI and PCT-MI participation may also be associated with some emotional discomfort, but this is not anticipated to be any more severe than the emotional discomfort associated with psychotherapy used in standard care.

Adverse events

Significant adverse events are not expected. For the purposes of this study, adverse events are defined as any newly identified medical diagnoses noted by medical personnel, or symptoms reported by the participant, which are *directly related to participation in the study and occur during the administration of testing/treatment or appear within two weeks of testing/treatment*. Participants will be instructed to contact the principal investigator if they believe they have potentially experienced an adverse event. Any adverse event will be reported to COMIRB by the PI in keeping with COMIRB regulations.

Risks

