As noted above, adverse events are not expected. The anticipated risks and discomfort associated with research procedures are not greater than those that would be ordinarily encountered during routine clinical care or psychological assessment, in which discussion of mental health and past traumatic events is the standard of care. Participants are at elevated risk for emotional distress and related sequelae by virtue of the fact that they have moral injury. For participants who reveal any imminent suicidality during the baseline assessment, or active suicidal ideation during the follow-up visits, the appropriate follow-up actions will be implemented by Drs. [name], [name], or other designated clinician with expertise in suicide risk assessment. Please see "Safety Monitoring" section below for more details. Participants also have the potential to become frustrated, fatigued, or distressed while completing study measures. Members of the research team will be trained to minimize psychological distress while assisting individuals in completing the protocol.

There is a potential loss of confidentiality and/or privacy. Minimizing risks to data security will be achieved by employing safeguards built into the framework of the VA Office of Research and Development (R&D).

Benefits

The primary benefit of this study is generalizable knowledge to help better understand the acceptability and feasibility of ACT for Moral Injury. Although ACT for Moral Injury is empirically informed, its efficacy has not been evaluated; therefore, no direct benefits to the

participants can necessarily be anticipated. Similarly, PCT-MI has not been used in a group format for moral injury and has not had its efficacy evaluated; therefore, direct benefits for participants in PCT-MI can not necessarily be anticipated.

Safety Monitoring

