The UWRAP will be used to assess and address any potential risk associated with participating in the study. In completing the UWRAP, participants will be asked to articulate pre-test potential stressors (Pre-Assessment Risk Assessment Questions). Following the assessment or treatment session, the UWRAP debriefing checklist and protocol will be administered. Using results from the debriefing, a trained member of the research team will evaluate responses and access additional assistance, if necessary. A trained clinical member of the research team would then conduct additional assessment of the participant's safety using the UWRAP and expertise in clinical suicide risk assessment.

Thus, a formal risk assessment protocol and standard operating procedure will be implemented for participants who endorse current suicidal ideation on the UWRAP or if the assessor is concerned about the participant's safety risk based on other statements made or responses to other assessment items.

Participants deemed to be at imminent risk for suicide will be referred to their clinician (if applicable) and/or be taken to Psychiatric Emergency Services, as indicated. If participation is occurring remotely (e.g., using videoconferencing) the study team will confirm the participant's physical location and address. If emergency services are needed, study staff and/or the MIRECC clinician on duty will assist the participant in accessing emergency services (e.g., by calling 911). Additionally, for participants deemed to be at imminent risk of suicide, imminent risk may be documented in their VA electronic medical record (e.g., by entering a note into their medical record). All research staff will be trained on the risk assessment protocol prior to enrolling or screening any participants. See Appendix 1 for a detailed Safety Monitoring Plan.

Additionally, contact information for the PI and COMIRB will be provided to all participants to report any potential adverse events.

Discontinuation of Study Participation

Study participation will be discontinued if any members of the study team determine that the participant meets exclusion criteria or the participant decides to withdraw from the study. For example, if a participant is unable to answer the postcard consent questions prior to the one or three month follow-up assessments, the session will be rescheduled or the participant will be unenrolled from the study, at the study team's discretion.

Data Security and Storage

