Appendix 1 Safety Monitoring Plan

UWRAP Protocol Guidelines, Decision Rules and Follow-up Procedures

Part I: Pre-risk Assessment of Suicidal Risk

Step 1: Using the Face Sheet, assess subject's mood and suicidality before administering measures or beginning an intervention

On a scale of 1 to 7:

- *what is your level of stress right now?*
- *what is your urge to harm yourself now?*
- *what is your intent to kill yourself right now?*
- *what is your urge to use drugs or alcohol right now?*

Step 2: Identify level of suicide risk

Examine participants' responses to suicide specific questions

- *what is your urge to harm yourself now?*
- *what is your intent to kill yourself right now?*

Step 3: Determine if further risk assessment is warranted

3a. If scores are greater than one, but less than or equal to 4 on either of the two suicide items, yet there are no apparent signs of distress or immediate concerns, continue with the research protocol and utilize the following strategies if needed:

- Pace the sessions**
- Check in with participant to see how they are doing**
- Allow more frequent breaks if needed**

3b. If participants' scores are greater than a 4 on either of the two suicide items

OR

Scores are equal to or less than 4 on either of the two suicide items, but participant appears distressed or exhibits other suicide signs or symptoms

Contact designated clinician to further evaluate risk

Step 4: Conduct further risk assessment if warranted

If indicated in step 3 above, the designated clinician will complete the Suicide Risk Assessment Worksheet (pg. 6-7 of the UWRAP)

Step 5: Initiate the appropriate follow up actions

Based on participant's responses on the suicide risk assessment worksheet, the designated clinician will initiate the appropriate follow up procedures. This may include:

- Referring the participant to the mental health clinic if not in treatment,
- Encouraging participant to check in with his/her mental health, primary care provider, or other health provider
- Walking the participant to urgent care (including Psychiatric Emergency Services) if risk is imminent or contacting 911.
- Continuing with the research protocol and utilizing the following strategies:
Pace the sessions

Check in with participant to see how they are doing
Allow more frequent breaks if needed

Part II: Debriefing Protocol Suicidal Risk

Step 1: Using the Debriefing Protocol, assess subject's mood and suicidality following administration of study measures

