***Note changes, and in particular, increase in suicidality from the pre-assessment risk**

Step 3: Determine if further risk assessment is warranted

3a. If scores are greater than one, but less than or equal to 4 on either of the two suicide items, yet there are no apparent signs of distress or immediate concerns

Encourage them to contact their mental health or primary care provider if needed

3b. If participants' score is greater than a 4 on either of the two suicide items **OR**

Scores are equal to or less than 4 on either of the two suicide items, but participant reports at least a two points increase since the pre-risk assessment, or appears distressed and exhibits other suicide signs or symptoms

Contact the designated clinician to further evaluate risk

Step 4: Conduct further risk assessment if warranted

If indicated in step 3b above, the designated clinician will complete the Suicide risk assessment worksheet (pg. 6-7 of the UWRAP)

Step 5: Initiate the appropriate follow up actions

Based on participant's responses on the suicide risk assessment worksheet, the designated clinician will initiate the appropriate follow up procedures. This may include:

- Referral to the MH clinic if not in treatment,
- Encouraging participant to check in with his/her mental health, primary care provider, or other health provider
- Walking the participant to urgent care (including Psychiatric Emergency Services) if risk is imminent or calling 911.
- Providing the participant with the VA national crisis hotline number

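### At suicide-item scores of 4 or less, the post-session rule in Appendix 1 leaves distress alone, or other suicide signs alone, without escalation unless a score has risen by two points

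*Combined protocol and SAP*

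**What the plan says.** Appendix 1 has two parallel decision rules based on the UWRAP, one before a session (Part I) and one after it (Part II). Each uses two suicide items scored 1 to 7, and in both parts a score above 4 on either item sends the case to the designated clinician. The rules differ at scores of 4 or less.

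- Part I Step 3b contacts the clinician when scores are in this range "but participant appears distressed or exhibits other suicide signs or symptoms".
- Part II Step 3b does so when the participant reports "at least a two points increase since the pre-risk assessment, or appears distressed and exhibits other suicide signs or symptoms".
- Part II Step 3a, the lower tier, applies to scores of 2 to 4 "yet there are no apparent signs of distress or immediate concerns". Its action is to encourage contact with a provider if needed.
- Part II Step 4 depends on the step before it: "If indicated in step 3b above, the designated clinician will complete the Suicide risk assessment worksheet".

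Safety Monitoring in section V adds a general provision. A formal risk protocol is used "for participants who endorse current suicidal ideation on the UWRAP or if the assessor is concerned" about safety, including from other statements or item responses. The same text then refers the reader onward: "See Appendix 1 for a detailed Safety Monitoring Plan".

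On follow-up, section IV.C (Safety Monitoring Measure) schedules the UWRAP at all assessments. Safety Monitoring requires a debrief after each assessment or treatment session and a location check when participation is remote. The one- and three-month follow-up paragraph in IV.C offers survey link and mail alongside phone or video. It lists the ASIQ among the measures but does not mention the UWRAP.

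**The concern.** A single conjunction separates the two rules, and it matters most after the session. Someone who becomes visibly distressed while completing measures, with low and stable suicide scores and no other signs, does not meet Part II Step 3b. Step 3a does not fit either, because it requires the absence of distress. Step 4 is then never reached. The same failure to escalate applies to someone who shows other suicide signs without visible distress.

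This situation is foreseeable. Section V states: "The main risk to participating in the study is potential emotional discomfort during the assessments". Under Risks it adds: "Participants also have the potential to become frustrated, fatigued, or distressed while completing study measures". A participant already distressed on arrival is caught by Part I. The practical gap is therefore distress or signs first seen during the session, which is what a debrief is there to detect. At stake is whether staff working through Appendix 1 step by step have an instruction for that case.

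**Working it through.** The plan gives no figure to reproduce. The check compares the two Step 3b rules state by state and then bounds how often the rule is used.

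**Inputs.** Cut-off of 4, the two-point rise, and the and/or wording: Appendix 1. 72 participants and the 30% loss-to-follow-up limit: section VII. Four assessments, twelve group sessions, and 10 minutes for the UWRAP: section IV.C.

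**Rule comparison, one suicide item.** Let pre- and post-session scores each run from 1 to 4, with distress yes/no and other signs yes/no: 4 × 4 × 2 × 2 = 64 states. A rise of at least two points occurs in 3 of the 16 score pairs (1→3, 1→4, 2→4), leaving 13 without one.

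| Rule applied after the session | Calculation | States escalated |
|---|---|---|
| Part I wording (distress or signs) | 16 × 3 | 48 |
| Part II wording (rise, or distress and signs) | 3 × 4 + 13 × 1 | 25 |
| Escalated by Part I wording only | 13 × 2 | 26 |
| Escalated by Part II wording only | 3 × 1 | 3 |
| Part II with *or* in place of *and* | 3 × 4 + 13 × 3 | 51 |

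The 26 are 13 with distress only and 13 with signs only, all without a two-point rise. The 3 are two-point rises with neither distress nor signs. The revised wording adds 51 − 25 = 26 states, so none is left that only the Part I wording escalates.

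**Both items together.** 4⁴ × 4 = 1,024 states. Those with distress alone or signs alone and no two-point rise on either item: 13 × 13 × 2 = 338. After the change: 0.

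**Cover from Safety Monitoring.** Assume that endorsing ideation on the UWRAP means a post-session score above 1. The no-rise pairs with a post-session score of 2, 3 or 4 number 4 + 3 + 2 = 9, so 9 × 2 = 18 of the 26 states are covered. The other 4 × 2 = 8, with a post-session score of 1, depend on assessor concern.

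**How often the rule is used.**
- Assessment debriefings: at most 72 × 4 = 288. With 30% loss at both follow-ups: 144 + 0.70 × 144 = 244.8, about 245.
- Treatment debriefings: at most 72 × 12 = 864 participant-sessions.

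**Secondary point.** Follow-up visits: at most 72 × 2 = 144, or 0.70 × 144 = 100.8 at 30% loss. The documents do not give the share done by mail or link. Assuming 10%, 25% or 50% of 100.8 gives about 10, 25 or 50 visits.

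**The case against.** The best counter-argument is that Appendix 1 is not the only safeguard. Under Safety Monitoring, a trained team member evaluates the debriefing results and seeks help if needed, and the formal risk protocol follows from endorsed ideation or assessor concern. Risks adds clinician action for active ideation at follow-up visits. An assessor who sees suicide signs would normally be concerned. It would therefore be wrong to infer that these participants have no route to a clinician. What remains is that the general triggers are absent from the stepwise rule to which Safety Monitoring sends staff, and that distress alone with scores of 1 depends entirely on judgement.

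A second argument is that the narrower limb may be deliberate. After a session there is a baseline score to compare with, and some discomfort is expected. That is coherent, but the documents do not say so. A deliberate narrowing would also be expected to place distress alone in Step 3a, and Step 3a excludes it.

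A third is burden. Debriefing also follows treatment sessions in a therapy about moral pain, and the change roughly doubles the escalating states, from 25 to 51. That cost is real, and its frequency cannot be estimated from the documents. The state count is unweighted and says nothing about how many participants are affected.

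Two stronger readings should be resisted. A reader might infer that the post-session rule is simply a weaker copy of the pre-session one. It is not, because its two-point-rise trigger has no counterpart in Part I and neither rule contains the other. A reader might also infer that mail or survey-link follow-up has no UWRAP, debrief or location check. The general requirements cover every assessment and all remote participation, an assessor is said to administer the follow-up measures, and a standard operating procedure that is not in the documents may hold the detail.

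**Conclusion.** The point holds in limited form. At scores of 4 or less, Part II Step 3b escalates on a two-point rise, or on distress together with other signs. Distress alone or signs alone, without that rise, is escalated by no Part II step. In the one-item enumeration this is 26 of 64 rule states. Section V covers 18 of them if a score above 1 counts as endorsed ideation, and the other 8 only through assessor concern. The finding rests on the wording of Appendix 1. The counts describe the logic of the rule and do not estimate participants at risk.

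The follow-up matter is a clarification only. The duties are stated in general terms, but the follow-up paragraph does not say how they are carried out when a form comes back by mail or link, and no time is given for reading returned ASIQ answers.

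**What to change.** In Appendix 1 Part II Step 3b, replace the *and* that joins distress to other suicide signs with *or*, and keep the two-point-rise trigger. This aligns the limb with Part I and closes all 26 states. It costs one word and some additional clinician contacts, spread over at most 288 assessment debriefings and 864 treatment participant-sessions. It needs no new staff role, since the designated clinician already serves the pre-session rule.

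As a secondary clarification, add to the follow-up paragraph in IV.C that any follow-up completed by mail or survey link is paired with a phone or video UWRAP and debrief, with location confirmed, and say when returned ASIQ answers are read. The team would have to set any ASIQ action threshold itself, because Appendix 1's numerical cut-offs apply to the UWRAP items.

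At the assumed 10 to 50 visits, a 10-minute UWRAP takes about 1.7 to 8.4 staff-hours over the trial (10.1 × 10/60 to 50.4 × 10/60), or 3.4 to 16.8 if the debrief takes a further 10 minutes (also an assumption). Since the UWRAP is already required at every assessment, this is largely time the plan already implies. Mail and link follow-up would become somewhat less convenient.
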